### **9.1.6. Case Report Forms**

For each subject consented, an eCRF casebook will be completed by an authorized study staff member whose training for this function is completed in EDC. The Inclusion/Exclusion Criteria and Enrollment eCRFs should be completed only after all data related to eligibility have been received. Subsequent to data entry, a study monitor will perform source data verification within the EDC system. System-generated or manual queries will be issued to the investigative site staff as data discrepancies are identified by the monitor or internal Gilead staff, who routinely review the data for completeness, correctness, and consistency. The site coordinator is responsible for

responding to the queries in a timely manner, within the system, either by confirming the data as correct or updating the original entry, and providing the reason for the update (e.g. data entry error). Original entries as well as any changes to data fields will be stored in the audit trail of the system. Prior to any interim time points or database lock (as instructed by Gilead), the investigator will use his/her log in credentials to confirm that the forms have been reviewed, and that the entries accurately reflect the information in the source documents. At the conclusion of the trial, Gilead will provide the site with a read-only archive copy of the data entered by that site. This archive must be stored in accordance with the records retention requirements outlined in Section 9.1.5.

#### **9.1.7.       Investigational Medicinal Product Accountability and Return**

Gilead recommends that used and unused IMP supplies be returned to the shipping facility from which it came for eventual destruction. The study monitor will provide instructions for return. If return is not possible, the study monitor will evaluate each study center's IMP disposal procedures and provide appropriate instruction for destruction of unused IMP supplies. If the site has an appropriate standard operating procedure (SOP) for drug destruction as determined by Gilead QA, the site may destroy used (empty or partially empty) and unused IMP supplies in accordance with that site's approved SOP. A copy of the site's approved SOP will be obtained for central files.

If IMP is destroyed on site, the investigator must maintain accurate records for all IMP destroyed. Records must show the identification and quantity of each unit destroyed, the method of destruction, and the person who disposed of the IMP. Upon study completion, copies of the IMP accountability records must be filed at the site. Another copy will be returned to Gilead.

The study monitor will review IMP supplies and associated records at periodic intervals.

#### **9.1.8.       Inspections**

The investigator will make available all source documents and other records for this trial to Gilead's appointed study monitors, to IRBs/IECs or to regulatory authority or health authority inspectors.

#### **9.1.9.       Protocol Compliance**

The investigator is responsible for ensuring the study is conducted in accordance with the procedures and evaluations described in this protocol.

### **9.2.           Sponsor Responsibilities**

#### **9.2.1.       Protocol Modifications**

Protocol modifications, except those intended to reduce immediate risk to study subjects, may be made only by Gilead. The investigator must submit all protocol modifications to the IRB/IEC in accordance with local requirements and receive documented IRB/IEC approval before modifications can be implemented.

## **9.2.2. Study Report and Publications**

A clinical study report (CSR) will be prepared and provided to the regulatory agency(ies). Gilead will ensure that the report meets the standards set out in the ICH Guideline for Structure and Content of Clinical Study Reports (ICH E3). Note that an abbreviated report may be prepared in certain cases.

Investigators in this study may communicate, orally present, or publish in scientific journals or other scholarly media only after the following conditions have been met:

The results of the study in their entirety have been publicly disclosed by or with the consent of Gilead in an abstract, manuscript, or presentation form or the study has been completed at all study sites for at least 2 years.

The investigator will submit to Gilead any proposed publication or presentation along with the respective scientific journal or presentation forum at least 30 days before submission of the publication or presentation.

No such communication, presentation, or publication will include Gilead's confidential information (see Section [9.1.4](#)).

The investigator will comply with Gilead's request to delete references to its confidential information (other than the study results) in any paper or presentation and agrees to withhold publication or presentation for an additional 60 days in order to obtain patent protection if deemed necessary.

## **9.3. Joint Investigator/Sponsor Responsibilities**

### **9.3.1. Payment Reporting**

Investigators and their study staff may be asked to provide services performed under this protocol, e.g. attendance at Investigator's Meetings. If required under the applicable statutory and regulatory requirements, Gilead will capture and disclose to Federal and State agencies any expenses paid or reimbursed for such services, including any clinical trial payments, meal, travel expenses or reimbursements, consulting fees, and any other transfer of value.

### **9.3.2. Access to Information for Monitoring**

In accordance with regulations and guidelines, the study monitor must have direct access to the investigator's source documentation in order to verify the accuracy of the data recorded in the eCRF.

The monitor is responsible for routine review of the eCRF at regular intervals throughout the study to verify adherence to the protocol and the completeness, consistency, and accuracy of the data being entered on them. The monitor should have access to any subject records needed to verify the entries on the eCRF. The investigator agrees to cooperate with the monitor to ensure that any problems detected through any type of monitoring (central, on site) are resolved.

### **9.3.3. Access to Information for Auditing or Inspections**

Representatives of regulatory authorities or of Gilead may conduct inspections or audits of the clinical study. If the investigator is notified of an inspection by a regulatory authority the investigator agrees to notify the Gilead medical monitor immediately. The investigator agrees to provide to representatives of a regulatory agency or Gilead access to records, facilities, and personnel for the effective conduct of any inspection or audit.

### **9.3.4. Study Discontinuation**

Both the sponsor and the investigator reserve the right to terminate the study at any time. Should this be necessary, both parties will arrange discontinuation procedures and notify the appropriate regulatory authority(ies), IRBs, and IECs. In terminating the study, Gilead and the investigator will assure that adequate consideration is given to the protection of the subjects' interests.

## 11. APPENDICES

- Appendix 1. Investigator Signature Page
- Appendix 2. Study Procedures Table
- Appendix 3. Management of Clinical and Laboratory Adverse Events
- Appendix 4. GSI Grading Scale for Severity of Adverse Events and Laboratory Abnormalities
- Appendix 5. Definitions of Stage 3 Opportunistic Illnesses in HIV (CDC Guidelines)
- Appendix 6. Pregnancy Precautions, Definition for Female of Childbearing Potential, and Contraceptive Requirements

**Appendix 2. Study Procedures Table**

Study Procedure	Screening a	Day 1 b	End of Week c						Post Week 48 d,v	30 Day Follow-Up e	ESDD f
			4	8	12	24	36	48			
Informed Consent	X										
Medical History	X										
Concomitant Medications	X	X	X	X	X	X	X	X	X	X	X
Adverse Events	X	X	X	X	X	X	X	X	X	X	X
Complete Physical Exam	X	X				X		X	X y		X
Symptom-Directed Physical Exam			X	X	X		X			X	
12-Lead ECG	X	X				X		X	X y		X
Height	X										
Weight	X	X	X	X	X	X	X	X	X	X	X
Vital Signs g	X	X	X	X	X	X	X	X	X	X	X
Urinalysis	X	X	X	X	X	X	X	X	X	X	X
Urine Chemistry h			X				X		X w		
Urine Pregnancy Test i			X	X	X	X	X	X	X	X	X
Serum Pregnancy Test i	X										
Chemistry Profile j	X	X	X	X	X	X	X	X	X	X	X
Metabolic Assessments k		X			X	X		X	X w		
Estimated GFR	X	X	X	X	X	X	X	X	X	X	X
Hematology Profile l	X	X	X	X	X	X	X	X	X	X	X
Plasma HIV-1 RNA m	X	X	X	X	X	X	X	X	X	X	X
CD4+ Cell Count	X	X	X	X	X	X	X	X	X	X	X
HBV Blood Panel	X n				X o	X o		X o,z	X o,z		
Plasma HBV DNA aa		X	X	X	X	X	X	X	X		X
HCVAb p	X							X	X y		
HCV RNA p	X					X		X	X w		

Study Procedure	Screening a	Day 1 b	End of Week c						Post Week 48 d,v Every 12 Weeks	30 Day Follow-Up e	ESDD f
			4	8	12	24	36	48			
HIV-1 Genotype/Phenotype g								X g			X g
Single PK Draw h				X		X	X				
Trough PK Draw h			X		X						
PK Sample (post-dose) h			X		X						
Observed In-Clinic Dose h			X		X						
Provide Dosing Diary h		X	X	X	X	X					
Collect Dosing Diary h			X	X	X	X	X				
Plasma Sample Storage h		X	X	X	X	X	X	X	X		X
Urine Sample Storage h		X	X	X	X	X	X	X	X		X
Whole Blood Storage Sample h		X									
PPD		X									
Randomization		X									
Study Drug Dispensation		X	X	X	X	X	X	X v	X v		
Study Drug Accountability			X	X	X	X	X	X	X		X

a Evaluations to be completed within 30 days prior to Day 1.

b Subjects should initiate dosing of study drug on the same day as the Day 1 visit.

c All study visits should be  $\pm$  2 days of the protocol-specified visit date based on the Day 1 visit through Week 12 and completed within  $\pm$  6 days at Week 24 and Week 36, unless otherwise specified. The visit window at Week 48 will be  $\pm$  6 weeks of the protocol-specified visit date.

d At the Week 48 Visit, subjects in a country where GS-9883/F/TAF FDC is not available will be given the option to receive GS-9883/F/TAF FDC for an additional 48 weeks, or until the product becomes accessible to subjects through an access program, or until Gilead Sciences elects to discontinue the study in that country, whichever occurs first. Study visits are to be completed every 12 weeks, within  $\pm$  6 days of the protocol-specified visit date unless otherwise specified.

e Must be completed 30 days after discontinuing study drug. For the purpose of scheduling a 30-Day Follow-Up Visit, a  $\pm$  6 days window may be used. Required for subjects who permanently discontinue study drug prior to Week 48 and do not continue in the study through at least one subsequent visit after the ESDD visit. Subjects who participate post Week 48 will be required to return to the clinic 30 days after the completion of study drugs for the 30-Day Follow-Up Visit.

f Early Study Drug Discontinuation visit to occur within 72 hours of last dose of study drug. Subjects will be asked to continue attending the scheduled study visits through the Week 48 Visit even if the subject discontinues study drug.

[figure not shown]
g Vital signs measurements including blood pressure, pulse, respiratory rate, and temperature

h Urine Chemistry includes urine albumin, urine creatinine, urine protein, retinol binding protein, and beta-2 microglobulin

i Women of childbearing potential only. Positive urine pregnancy tests will be confirmed with a serum test.

- j Chemistry profile: alkaline phosphatase, AST, ALT, GGT, total bilirubin, direct and indirect bilirubin, total protein, albumin, bicarbonate, BUN, calcium, chloride, creatinine, glucose, phosphorus, magnesium, potassium, sodium, uric acid, and amylase (reflex lipase testing is performed in subjects with total amylase  $> 1.5 \times \text{ULN}$ ). At Day 1, Weeks 24, and 48 and every 24 weeks during the post Week 48 period, analyses of glucose will be done as part of the fasting metabolic assessments and not as part of the chemistry profile. TSH will be collected at Screening, Day 1, Weeks 24, and 48, as well as every 24 weeks post Week 48, and ESDD if applicable. PT/INR will be performed at Day 1.
- k Fasting glucose and lipid panel (total cholesterol, HDL, direct LDL, triglycerides). If the subject has not fasted prior to the visit, the visit may proceed, but the subject must return within 72 hours in a fasted state to draw blood for the metabolic assessments.
- l CBC with differential and platelet count.
- m If the HIV-1 RNA value is  $\geq 50$  copies/mL at Week 48, a retest HIV-1 RNA value must be collected within two to three weeks of the initial test.
- n Hepatitis B Virus (HBV) blood panel will be performed at screening: Hepatitis B virus surface antigen (HBsAg), Hepatitis B virus surface antibody (HBsAb) and Hepatitis B virus core antibody (HBcAb). If positive HBsAg, reflex testing for plasma HBV DNA, HBeAg (if negative, reflex HBeAb), and quantitative HBsAg. If positive HBcAb with negative HBsAg and negative HBsAb, reflex testing for plasma HBV DNA (if positive, reflex HBeAg). If HBeAg is performed and found to be negative, reflex HBeAb.
- o At Weeks 12, 24, 48, 72, and 96, for subjects who meet the definition of HBV infection at any visit, the following will be conducted by the central laboratory: HBsAb, HBsAg (qualitative and quantitative) and HBeAg (if negative, reflex HBeAb).
- p Subjects who are HCVAb positive at screening or at Week 48 will have a HCV RNA test performed at screening or at Week 48 and every 24 weeks thereafter. Subjects who are HCVAb positive at the Week 96 visit will also have a HCV RNA test performed.
- q HIV-1 genotype/phenotype testing for subjects with HIV-1 RNA  $\geq 200$  copies/mL and virologic rebound, at early study drug discontinuation or Week 48. Following unconfirmed virologic rebound, subjects will be asked to return to the clinic (2-3 weeks later) prior to the next scheduled visit or at the next scheduled study visit, for a HIV-1 RNA and HIV-1 genotype/phenotype (reverse transcriptase, protease and integrase) blood draw. Based on the results of this testing, subjects should be managed according to the Virologic Rebound Schema (Section 6.13.1).
- r All subjects on GS-9883/F/TAF (Treatment Group 1 only) will have a single anytime PK blood sample collected at Weeks 8, 24 and 36.
- s Subjects on GS-9883/F/TAF (Treatment Group 1 only) will have a Trough PK blood sample collected between 20-28 hours following their last dose at Weeks 4 and 12. Subjects must be instructed to not take their study drugs on the morning of their visit for the trough sample collection. If the subject has taken their dose of study drugs prior to the visit, the visit may proceed, but the subject must return within 72 hours for the single trough PK blood sample collection. In the event a subject routinely takes their study drug in the evening, a single anytime sample may be drawn at Weeks 4 and 12 as the subject will not be instructed to change their dosing time to accommodate this trough PK draw. A post-dose PK blood sample will be collected between 1 and 4 hours post dose following an observed, in-clinic dose.
- t Plasma storage samples banked for possible future protocol-related testing (safety, virology, pharmacokinetic analysis). Urine storage samples banked for possible future protocol-related safety testing including urine chemistry. Whole blood sample for potential virologic resistance testing and/or HIV DNA genotyping. **PPD**
- u A dosing diary will be dispensed for all Treatment Group 1 subjects to complete prior to each of the PK sample visits.
- v Open-label GS-9883/F/TAF FDC will be dispensed to subjects participating in the study post Week 48 starting at the Week 48 Visit.
- w Every 24 weeks only.
- x Dosing diaries will be collected from subjects for the single anytime PK and trough PK collection (Treatment Group 1 only). If a dosing diary is not returned the site may ask the subject for the time of the last dose and if it was taken with or without food.
- y To be performed every 48 weeks post Week 48 visit.
- z At Weeks 48 and 96, for subjects who do **NOT** meet the definition of HBV infection at any visit, the following will be performed by the central laboratory: HBsAb, HBcAb, and HBsAg. Subjects who are not HBsAg and/or HBcAb positive will have a reflex test for HBV DNA (viral load).
- aa To be performed for subjects who meet the definition of HBV infection.

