### **6.13.1. Management of Virologic Rebound**

Subjects who meet the criteria listed below will be considered to have virologic rebound:

- At any post Day 1 visit, a rebound in HIV-1 RNA  $\geq 50$  copies/mL, which is subsequently confirmed at the following scheduled or unscheduled visit;

OR

- Any subject with HIV RNA  $\geq 50$  copies/mL at study drug discontinuation

Following the unconfirmed virologic rebound, subjects will be asked to return to the clinic for a scheduled or unscheduled blood draw (2 to 3 weeks after the date of the original test that resulted in HIV-1 RNA virologic rebound) for confirmation of virologic rebound. If virologic rebound is confirmed at the scheduled or unscheduled visit and the HIV-1 RNA is  $\geq 200$  copies/mL, the

blood sample from the confirmation visit will be the primary sample used for HIV-1 genotypic and phenotypic testing. Subjects with documented non-adherence within 72 hours of the visit may not be tested for resistance. After a subject's first post-Day 1 resistance test, additional testing will be conducted on a case-by-case basis. Any subject may be discontinued at Investigator's discretion or per local treatment guidelines.

[figure not shown]
If no resistance is detected from the genotype or phenotype, the subject may remain on study drugs and a repeat HIV-1 RNA should be repeated (2 to 3 weeks after date of test with HIV-1 RNA  $\geq$  50 copies/mL). Investigators should carefully evaluate the benefits and risks of remaining on study drug for each individual subject and document this assessment in the on-site medical record.

Subjects who are noncompliant on an ongoing basis will be considered for discontinuation per the Investigator's discretion or local treatment guidelines. Investigators who opt to discontinue study drugs for an individual subject must discuss with the Medical Monitor prior to study drug discontinuation.

For subjects who are off study drug but remain on study, it will be the Investigator's discretion to manage virologic rebound.

Please refer to [Figure 6-1](#) for the management of subjects who meet the criteria for virologic rebound.

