**Figure 6-1. Virologic Rebound Schema**

- a If virologic rebound is not confirmed, the subject will remain on their current regimen.
- b If virologic rebound is confirmed and the HIV-1 RNA is  $\geq 200$  copies/mL, the HIV-1 genotype and phenotype (reverse transcriptase, protease, and integrase) will be analyzed.
- c Based on the results of the genotype and phenotype assays, the subject will remain on study drugs or study drugs will be discontinued. If genotyping or phenotyping fails, a new ARV regimen may be configured at the discretion of the Investigator.
- d If no resistance is detected, HIV-1 RNA will be repeated (2-3 weeks later). Investigator reviews study drug continuation/discontinuation options and discuss with the Medical Monitor prior to study drug discontinuation.
- e A new ARV regimen will be configured, at the Investigator's discretion, and the subject will remain in the study.

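### Appendix 2 footnote q lets a rebound be confirmed at the next scheduled visit, nominally 12 weeks away from Week 12 on, while Section 6.13.1 asks for the draw at 2 to 3 weeks

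*Protocol*

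**What the plan says.** **Protocol Section 6.13.1 (procedure).** After an unconfirmed rebound, the woman is asked back for a scheduled or unscheduled draw, timed "2 to 3 weeks after the date of the original test that resulted in HIV-1 RNA virologic rebound". If the rebound is confirmed at 200 copies/mL or more, the "blood sample from the confirmation visit will be the primary sample used for HIV-1 genotypic and phenotypic testing".

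**Protocol Appendix 2, footnote q.** For the same situation, "subjects will be asked to return to the clinic (2-3 weeks later) prior to the next scheduled visit or at the next scheduled study visit". The footnote then refers to the rebound schema for management once results are available. SAP Appendix 1 repeats it.

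**Protocol Figure 6-1, notes b and c.** With a confirmed value of at least 200 copies/mL, "the HIV-1 genotype and phenotype (reverse transcriptase, protease, and integrase) will be analyzed". Note c then makes the treatment decision depend on that result: "Based on the results of the genotype and phenotype assays, the subject will remain on study drugs or study drugs will be discontinued".

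**Protocol Appendix 2, footnote m.** For a Week 48 value of 50 copies/mL or more, "a retest HIV-1 RNA value must be collected within two to three weeks of the initial test". It offers no next-visit alternative.

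**The concern.** Section 6.13.1 and footnote q both tell the site when to take the same blood sample, and they differ. In Section 6.13.1 the 2-to-3-week timing governs the draw whether it is scheduled or unscheduled. In footnote q that timing sits with the first alternative, and the second is the next scheduled visit, whenever that falls. A site working from the procedures table could see a first value at Week 12, wait until Week 24 to confirm it, and comply with the footnote while missing the Section 6.13.1 draw.

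What is at stake is patient management:

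- Confirmation comes later.
- At a confirmed 200 copies/mL or more, genotype and phenotype testing and the decision to stay on or stop study drug come later too.
- At a confirmed 50–199 copies/mL no genotype is triggered, so only confirmation is delayed.

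No difference between the arms is suggested.

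**Working it through.** **Inputs**

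- Target interval: 2 to 3 weeks = 14–21 days (Protocol Section 6.13.1).
- Visits: Weeks 4, 8, 12, 24, 36 and 48 (Protocol Synopsis and Section 6.4), then every 12 weeks = 84 days in the extension (Section 6.5.1).
- Windows: ±2 days through Week 12, ±6 days at Weeks 24 and 36, ±6 weeks = ±42 days at Week 48, ±6 days in the extension (Sections 6.4 and 6.5.1; Appendix 2 footnotes c and d).

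**Formulas**

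- Nominal gap = (next week − current week) × 7.
- Gap range = nominal gap − (sum of the two windows) to nominal gap + (sum of the two windows).
- Extra delay, nominal = gap − 21 to gap − 14.
- Extra delay, with windows = smallest gap − 21 to largest gap − 14.

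**Results (days)**

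| First value at | Next visit | Nominal gap | Gap with windows | Extra delay, nominal | Extra delay, with windows |
|---|---|---|---|---|---|
| Week 4 | Week 8 | 28 | 24–32 | 7–14 | 3–18 |
| Week 8 | Week 12 | 28 | 24–32 | 7–14 | 3–18 |
| Week 12 | Week 24 | 84 | 76–92 | 63–70 | 55–78 |
| Week 24 | Week 36 | 84 | 72–96 | 63–70 | 51–82 |
| Week 36 | Week 48 | 84 | 36–132 | 63–70 | 15–118 |
| Extension visit (Week 60 on) | Next extension visit | 84 | 72–96 | 63–70 | 51–82 |

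Worked example, Week 36: (48 − 36) × 7 = 84. The windows add or subtract 6 + 42 = 48, giving 36 to 132. The extra delay is 36 − 21 = 15 to 132 − 14 = 118.

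**Can both alternatives be read as limited to 2 to 3 weeks?** The smallest gap in the table is 24 days and the upper end of the target is 21. No row overlaps 14–21. On that reading, the second alternative could never apply to a value first seen at an in-window scheduled visit. It would apply only when the first value came from an unscheduled draw that happened to fall 14–21 days before a scheduled visit.

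**How much of the schedule is affected?** Of the five post-Day 1 visits before Week 48 (Weeks 4, 8, 12, 24 and 36), three are followed by the 12-week gap. There the wait under the second alternative is 84/21 = 4 to 84/14 = 6 times the intended one.

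**Downstream timing when no resistance is found.** A further HIV-1 RNA is then due 2 to 3 weeks later. Assuming this is counted from the confirmation test, the time from first value to this follow-up is:

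- under Section 6.13.1: 14 + 14 = 28 to 21 + 21 = 42 days;
- under the footnote's second alternative, after a 12-week gap: 84 + 14 = 98 to 84 + 21 = 105 days (nominal).

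**The case against.** The strongest reply is that the next-visit route is already in Section 6.13.1. Its definition of rebound accepts confirmation at the following scheduled or unscheduled visit and sets no time limit. The word scheduled in the Section 6.13.1 procedure is also nearly empty, for the same arithmetic reason, so emptiness alone cannot rule out reading the footnote's timing as covering both alternatives. The treatment sections (6.4 and 6.5.1) send sites to Section 6.13.1, and every explicit interval given for this draw is 2 to 3 weeks. A late confirmation would also remain possible under any sensible fix. On this view, the difference is one of drafting.

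Part of this stands. The definition is open-ended, and the footnote is not the only loose wording. The 118-day upper end needs Week 36 at its earliest and Week 48 at its latest in the same woman. The boxes of Figure 6-1 are not in the available text, so nothing can be said about them.

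It does not remove the conflict. The definition states what counts as confirmed; the procedure states when to draw, and its timing plainly covers both kinds of draw. Footnote q is also an instruction on when to draw, and it joins an untimed alternative with *or*. Section 6 presents the table and the text as two accounts of the same procedures, and no rule was found that gives the text precedence. A site can follow the footnote literally and miss the draw.

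The consequences are limited. Investigators may act sooner: "Any subject may be discontinued at Investigator's discretion or per local treatment guidelines". The snapshot algorithm in Section 8.5.1.1 does not use confirmation of rebound.

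**Conclusion.** The concern holds, as a minor one. Footnote q permits a confirmatory draw later than the Section 6.13.1 procedure asks for whenever the first value comes from an in-window scheduled visit before Week 48 or in the extension. Nominally the draw is 1–2 weeks late after Weeks 4 and 8 and 9–10 weeks late from Week 12 on.

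This assumes that visits fall within their windows and that a site takes the footnote's second alternative. Week 48 values are excluded because footnote m covers them. The documents give no expected number of unconfirmed rebounds, so no count of affected women is offered.

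**What to change.** In Protocol Appendix 2, footnote q, replace the timing clause with: *at a scheduled or unscheduled visit 2 to 3 weeks after the original test; if that draw is missed, at the next available visit*. This matches the Section 6.13.1 procedure and makes the later visit a fallback instead of an equal choice. Leave the Section 6.13.1 definition of rebound as it is, so that a late confirmation still counts. Update the copy in SAP Appendix 1 for consistency; it does not direct sites.

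The cost is one clause in one footnote. The only added burden is a few unscheduled draws that Section 6.13.1 already requests.

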## **6.13. Virologic Failure**

Virologic failure is defined as virologic rebound or having HIV-1 RNA  $\geq 50$  copies/mL at study drug discontinuation or Week 48.

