### **6.13.2. Subjects with HIV-1 RNA $\geq 50$ copies/mL at Study Discontinuation or Week 48**

Subjects with HIV-1 RNA  $\geq 50$  copies/mL at study drug discontinuation or last visit will be considered virologic failures. Subjects with HIV-1 RNA  $\geq 50$  copies/mL at Week 48 will be asked to return for an unscheduled visit within the visit window for a retest.

Subjects with HIV-1 RNA  $\geq 200$  copies/mL at study drug discontinuation, last visit or Week 48 will also have resistance testing conducted.

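### Week 48 resistance testing has three different triggers, and the primary sample from SBR women who enter the extension may be drawn on B/F/TAF

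*Protocol*

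**What the plan says.** **Trigger at Week 48.** Three places set it.

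- Appendix 2, footnote q, attached to the genotype/phenotype row, asks for HIV-1 RNA of at least 200 "copies/mL and virologic rebound, at early study drug discontinuation or Week 48".
- Protocol 6.13.2 asks only for the value: women at 200 or more "copies/mL at study drug discontinuation, last visit or Week 48 will also have resistance testing conducted". It requires no confirmation and names no sample.
- Protocol 6.4 lists the test at Week 48 for virologic failure, with no 200 threshold. Section 6.13 supplies the definition: "Virologic failure is defined as virologic rebound or having HIV-1 RNA" of at least 50 copies/mL at study drug discontinuation or Week 48.

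**What rebound means.** Under 6.13.1 it is a value of at least 50 copies/mL "which is subsequently confirmed at the following scheduled or unscheduled visit". A value of at least 50 at study drug discontinuation also counts, without confirmation.

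**Which sample.** If rebound is confirmed and HIV-1 RNA is at least 200, 6.13.1 says that the "blood sample from the confirmation visit will be the primary sample used for HIV-1 genotypic and phenotypic testing". Further tests after a woman's first post-Day 1 resistance test are decided case by case. Footnote q likewise puts the resistance draw at the return visit. For a raised Week 48 value, footnote m says that "a retest HIV-1 RNA value must be collected within two to three weeks of the initial test".

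**When the regimen changes.** Footnote v of the same table: "Open-label GS-9883/F/TAF FDC will be dispensed to subjects participating in the study post Week 48 starting at the Week 48 Visit". Protocol 6.5.1 limits the extension to women who completed 48 weeks in a country where the product is not available. It sets no HIV-1 RNA condition and no wait for the Week 48 result. SAP 3.2 confirms that SBR women in the extension change to B/F/TAF.

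**What is stored.** Protocol 6.4 and footnote t provide for plasma stored at each visit, Week 48 included, with virology among its stated uses.

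**The concern.** There are two linked problems.

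1. The three triggers disagree on who is tested. A site working from the procedures table would follow footnote q and could withhold a test that 6.13.2 requires. This applies to both arms.
2. The sample rule works unevenly between arms at the moment of switching. A woman randomised to B/F/TAF who is first raised at Week 48 is retested on the drug she was already taking. An SBR woman who enters the extension is retested after she has been given a different regimen. Her retest may be suppressed, so that no test follows under 6.13.1, or it may show virus selected under B/F/TAF as well as SBR.

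At stake is a resistance result for virus that failed on SBR, and the correct attribution of any mutation found.

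**Working it through.** **1. Triggers side by side.** Take a woman not raised before Week 48, and read each rule literally.

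| Week 48 value | Retest at 2–3 weeks | Footnote q | 6.13.2 | 6.4 with 6.13 |
|---|---|---|---|---|
| 50–199 | 50–199 | no test | no test | test |
| ≥ 200 | < 50 | no test (not confirmed) | test | test |
| ≥ 200 | 50–199 | unclear: rebound confirmed, but 6.13.1 asks for ≥ 200 | test | test |
| ≥ 200 | ≥ 200 | test | test | test |

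The rules agree only in the last row.

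**2. Timing.** Nominal Week 48 is 48 × 7 = Day 336. A retest 14 to 21 days later falls on Days 350 to 357. If the first extension dose is taken when the drug is dispensed, the retest follows about 2 to 3 weeks of B/F/TAF. Same-day dosing is inferred: the protocol requires it at Day 1 but has no such line for the extension, and nothing provides for a delay.

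**3. What the retest could miss (illustration only).** Protocol 1.2.3.2 gives a mean change of −2.06 log10 at Day 11 on 50 mg GS-9883 alone (4 subjects, fasted) and a time-weighted average of −1.37 log10. The Week 48 value that would fall to a threshold T is T × 10^fall:

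- fall 2.06: 50 × 10^2.06 = 5,741; 200 × 10^2.06 = 22,963
- fall 1.37: 50 × 10^1.37 = 1,172; 200 × 10^1.37 = 4,688

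Susceptible virus below about 4,700 to 23,000 copies/mL at Week 48 could therefore be under the 200 needed for genotyping at the retest. Below about 1,200 to 5,700, the rebound would not be confirmed either. This assumes the same fall from a lower starting level.

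**4. How many women.** Protocol 8.8 gives 235 per group, 2% with the primary outcome in each, a 4% margin and one-sided 0.025. Its power figure reproduces: Φ(0.04/√(2 × 0.02 × 0.98/235) − 1.96) = 0.872, against the stated 87%. Only the 2% and the 235 are used here.

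- SBR women at 50 or more at Week 48: 235 × 0.02 = 4.7 expected; 95% binomial range 1 to 9. This is an upper figure, because the snapshot outcome also counts some discontinuations.
- Affected by the sample rule: they must also be first raised at Week 48, be at 200 or more, and enter the extension. The documents give none of these shares. Assuming the same share s for each, the expected number is 4.7 × s³:

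| s (assumed) | Expected women | P(at least one) |
|---|---|---|
| 0.25 | 0.07 | 0.071 |
| 0.50 | 0.59 | 0.445 |
| 0.75 | 1.98 | 0.863 |

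**The case against.** The strongest reply is that 6.13.2 is written for this case. It is the specific Week 48 rule, it requires testing at 200 or more without confirmation, and the ordinary reading is that it prevails over the general rule in 6.13.1. The procedures table marks the test at Week 48 and not in the post-Week 48 column. The on-SBR blood is not lost, since plasma is stored, and 6.13.1 calls the confirmation sample primary, not exclusive.

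Much of this stands. A woman tested under 6.13.2 on her Week 48 sample is unaffected. So is a woman whose earlier raised value is confirmed at Week 48 while she is still on SBR. The table mark does not settle the matter, however: it carries footnote q, which adds the rebound condition and places the resistance draw at the return visit. Section 6.13.2 does not say which sample to use. If the on-B/F/TAF sample is tested first, a later test of the stored one is discretionary.

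The end of SBR at Week 48 could also be read as study drug discontinuation, which would make a single value a rebound. The text does not say so, and 6.5.1 describes these women as having completed treatment.

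A reader might infer more than the documents support:

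- *That SBR virus cannot be tested.* It can, under 6.13.2 or from stored plasma.
- *That viraemia at the switch goes unseen.* SAP 5.2 tabulates HIV-1 RNA below 50 against 50 or more at the B/F/TAF baseline.
- *That the efficacy comparison is affected.* Resistance is not an objective or endpoint in Protocol sections 2 and 3.1.
- *That extension entrants must be rechecked against inclusion criterion 14.* That is a criterion for study entry, and no action is attached to such a review.

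**Conclusion.** The point holds as a small wording defect with a practical consequence. The three Week 48 triggers are incompatible in both arms: an unconfirmed value of 200 or more is tested under 6.13.2 and not under footnote q. For SBR women first raised at Week 48 who enter the extension, the 6.13.1 sample rule can select blood drawn on B/F/TAF. Resistance that arose on SBR can then be missed or misattributed unless 6.13.2 is applied to the Week 48 sample.

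The size is small. The upper figure is about 4.7 of 235 SBR women. The narrower range of 0.07 to 2.0 rests wholly on assumed shares and spans 27-fold ((0.75/0.25)³). The sample part also rests on the inference that B/F/TAF is started when dispensed. No primary or secondary analysis changes.

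**What to change.** Make four wording changes.

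1. Footnote q: for Week 48, remove the virologic-rebound condition, so that a single value of 200 copies/mL or more is enough, as in 6.13.2.
2. Section 6.4: add the 200 copies/mL threshold to the Week 48 genotype/phenotype bullet.
3. and 4. Sections 6.13.1 and 6.13.2: state that, for subjects entering the extension, the stored Week 48 plasma is the primary genotype/phenotype sample.

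Dispensing at the Week 48 Visit stays as it is.

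The cost is a few assays: at most about 4.7 expected in the SBR arm and 470 × 0.02 = 9.4 in both arms, fewer at 200 or more. Some will be on values that a retest would not have confirmed, which 6.13.2 already accepts. No patients, visits or blood draws are added. It assumes that the stored plasma volume is enough for the assay; the documents do not give the volume.
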